Procedures entail administration of medications, collection of blood and urine, buccal swab for genotyping analyses, and pharmacologic biomarker analysis. Subjects fulfilling eligibility criteria and providing informed consent at the screening visit (study visit 1) will arrive to the UW ITHS Adult Translational Research Unit (TRU) for each of the 4 study visits: twice before (study visits 2 and 6; pre-hormone treatment control days) and twice after sequential treatment with estradiol and cortisol (study visits 4 and 8; post-hormone treatment days). A baseline blood draw (time 0 hr) will be performed (24 mL of blood) to establish baseline levels of cortisol and estradiol and collect peripheral blood mononuclear cells (PBMCs). At the pre-treatment pharmacokinetic study visits, subjects will take a single dose of dronabinol (2.5 mg PO). The subjects will then collect their urine for 24 hours. Additionally, after placement of an intravenous catheter, venous blood samples (2-4 mL per time point) will be collected at 0.5, 1, 1.5, 2, 3, 4, 6, 8, 10, 12 and 24 hours after THC dosing. The total volume of blood drawn will not exceed 75 mL. At each time point, pharmacological biomarker analysis will also be performed. Heart rate changes will be recorded as an objective measure of pharmacologic effects of dronabinol. At each time point, participants will also complete a questionnaire describing subjective effects related to mood, drug effect, and physical symptoms using a visual analog scale (VAS). After a minimum washout period of one week, the subject will have an estradiol patch applied for one week, delivering 0.3 mg/day or take hydrocortisone twice daily by mouth (30 mg/day; 20 mg in the morning and 10 mg in the afternoon) for one week prior to returning to the clinic for the post-treatment pharmacokinetic study visits. Dronabinol dosing, urine and blood sampling, and pharmacological analysis will be identical to that performed on the first study visit. Subjects will leave the TRU after the 12-hour timepoint for each pharmacokinetic study and present to the Center for Research in Reproduction and

Contraception (CRRC) for a study visit the following morning (study visits 3, 5, 7, and 9) to return the 24-hour urine collection and undergo blood sampling at the 24-hour timepoint.

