The primary outcome measure of the study will be the change in the area under the plasma concentration-time curve (AUC) of THC following each of the interventions: exogenous estradiol and hydrocortisone exposures.

Estradiol phase:

Primary Outcome 1: Determination of whether estradiol alters THC exposure

The primary outcome is to determine whether the exposure to THC (as determined by AUC) is altered consequent to estradiol treatment when compared to the pre-treatment control and to quantify the magnitude of the change.

Secondary Outcome 1: Determination of whether other pharmacokinetic parameters of THC and its metabolites are different as a consequence of estradiol treatment

We will determine the time to peak concentration of THC, the peak concentration of THC, and the half-life of THC before and after estradiol treatment. We will also determine the AUC of metabolites of THC (11-OH-THC, 11-nor-COOH-THC, the glucuronides of 11-OH-THC and 11-nor-COOH-THC) before and after estradiol treatment. We will calculate the fraction of THC dose excreted into urine in the form of each of the metabolites and the renal clearance of each of the compounds based on urine and plasma data.

Secondary Outcome 2: Determination of the magnitude of effect of THC on heart rate in the presence and absence of estradiol treatment

As an objective measure of the pharmacologic effects of dronabinol, subjects will undergo monitoring of heart rate. The change in heart rate will be reported for each time point after dosing in comparison to baseline. The time course of change in heart rate will be reported and the change in heart rate at each time point after baseline will be compared to baseline. These data will be used as a descriptive measure of the magnitude and duration of the pharmacological effects of THC and to explore whether the doses used are pharmacologically active.

Secondary Outcome 3: Description of the side effects and psychoactive effects caused by THC in the presence and absence of estradiol treatment

Subjects will be asked to rate subjective effects related to mood, drug effect, and physical symptoms using a VAS as a function of time after dronabinol dosing. Subjects will complete VAS ratings at each of the blood sampling timepoints during the pharmacokinetic study visits.

Hydrocortisone phase:

Primary Outcome 1: Determination of whether hydrocortisone alters THC exposure

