The primary outcome is to determine whether exposure to THC (as determined by AUC) is altered consequent to hydrocortisone treatment when compared to the pre-treatment control and to quantify the magnitude of the change.

Secondary Outcome 1: Determination of whether other pharmacokinetic parameters of THC and its metabolites are different as a consequence of hydrocortisone treatment

We will determine the time to peak concentration of THC, the peak concentration of THC, and the half-life of THC before and after estradiol treatment. We will also determine the AUC of metabolites of THC (11-OH-THC, 11-nor-COOH-THC, the glucuronides of 11-OH-THC and 11-nor-COOH-THC) before and after hydrocortisone treatment. We will calculate the fraction of THC dose excreted into urine in the form of each of the metabolites and the renal clearance of each of the compounds based on urine and plasma data.

Secondary Outcome 2: Determination of the magnitude of effect of THC on heart rate in the presence and absence of hydrocortisone treatment

As an objective measure of the pharmacologic effects of dronabinol, subjects will undergo monitoring of heart rate. The change in heart rate will be reported for each time point after dosing in comparison to baseline. The time course of change in heart rate will be reported and the change in heart rate at each time point after baseline will be compared to baseline. These data will be used as a descriptive measure of the magnitude and duration of the pharmacological effects of THC and to explore whether the doses used are pharmacologically active.

Secondary Outcome 3: Description of the psychoactive effects and side effects caused by THC in the presence and absence of hydrocortisone treatment

Subjects will be asked to rate subjective effects related to mood, drug effect, and physical symptoms using a VAS as a function of time after dronabinol dosing. Subjects will complete VAS ratings at each of the blood sampling timepoints during the pharmacokinetic study visits.

Inclusion and Exclusion Criteria:

Inclusion Criteria

- a. Healthy, premenopausal women ages 21-45 years old
- b. Normal menstrual cycles (monthly, cycles 28-35 days in length)
- c. Body mass index $<30 \text{ kg/m}^2$
- d. Must be willing to use nonhormonal methods to avoid conception during the study period

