The changes in AUCs and formation clearances of metabolite parameters (the AUCs of the metabolites, and the formation clearances of each metabolite) will be tested using paired analysis of variance on log-transformed data with each subject serving as her own control.

The change in heart rate will be reported for each time point after dronabinol dosing in comparison to baseline. The time course of change in heart rate will be reported and the change in heart rate at each time point after baseline will be compared to baseline by repeated-measures ANOVA.

We will report the nature of observed psychoactive effects and the mean absolute VAS score for all the subjects at the specific time points in the two different study sessions (pre- and post-hormone treatment). The change in each subjective measure will also be reported for each time point after dosing in comparison to baseline. The time course of change in each subjective measure will be reported, and the change in each subjective measure at each time point after baseline will be compared to baseline by repeated-measures ANOVA.

5. QA and QC plan

Blood and urine samples and buccal swabs will be obtained directly from study participants. The samples will be labeled with a unique sample code that is linked to the donor, the type of specimen and the sampling date. Coded sample records are kept in a password protected computer and backed up on an independent computer server. We will obtain the sample code, collection date and time, drug administration records and sample volume data for each subject.

Valid QC procedures for authentication of the chemicals used in quantitative analysis and for quality assurance will be employed for all assays used for the proposed studies.

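### No estimate or test of the hormone-versus-control difference is planned for heart rate or VAS, although both secondary outcomes are framed as THC's effect with and without the hormone

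*Combined protocol and SAP*

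**What the plan says.** The outcome definitions are in section 2, under the primary and secondary objectives. Secondary Outcome 2 of the estradiol phase is "Determination of the magnitude of effect of THC on heart rate in the presence and absence of estradiol treatment", and the hydrocortisone phase has the parallel "Determination of the magnitude of effect of THC on heart rate in the presence and absence of hydrocortisone treatment". Secondary Outcome 3 of the estradiol phase is "Description of the side effects and psychoactive effects caused by THC in the presence and absence of estradiol treatment", again with a hydrocortisone counterpart. The text under Outcome 2 limits its use: "These data will be used as a descriptive measure of the magnitude and duration of the pharmacological effects of THC", together with exploring whether the doses are pharmacologically active.

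The methods are in section 4, Statistical analysis plan. For heart rate, "the change in heart rate at each time point after baseline will be compared to baseline by repeated-measures ANOVA". For VAS, "the change in each subjective measure at each time point after baseline will be compared to baseline by repeated-measures ANOVA". The plan also reports "the mean absolute VAS score for all the subjects at the specific time points in the two different study sessions (pre- and post-hormone treatment"). That sentence covers reporting only; no paired difference or interval is attached to it. Heart rate has no equivalent sentence on reporting by session.

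In the same section, the AUCs of THC and its metabolites are compared between treatment and control by a paired analysis on the log scale.

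**The concern.** The outcome titles ask how THC's effect compares with and without the hormone. The planned ANOVA asks whether a measure moves away from baseline after dosing. No session factor, session-by-time term or paired post-versus-control difference is named for either measure.

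The data would support the comparison, because section 2 makes dosing, sampling and pharmacological assessment the same before and after hormone treatment. If the plan is followed as written, the report will show time courses and within-session tests. A reader who wants to know whether the hormone changed the response will have only those to compare by eye. Noting that a time point is significant in one session and not in the other is not a valid test of the difference between sessions.

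**Working it through.** **Question and method, side by side**

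| Measure | Question in section 2 | Test in section 4 | Between-session estimate, interval or test |
|---|---|---|---|
| THC AUC | Altered by the hormone? | Paired, treatment versus control | Yes |
| Metabolite AUCs | Different as a result of the hormone? | Paired within subject | Yes |
| Heart rate | Size of THC effect with and without the hormone | Time point versus baseline | None |
| VAS | Description of effects with and without the hormone | Time point versus baseline | None; means shown for both sessions |

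**Which baseline.** Section 4 does not define it. Section 2 uses the word for time 0 ("A baseline blood draw (time 0 hr) will be performed"), and section 4 speaks of change after dosing, so time 0 of the same session is the natural reading. The Table of Study Events, however, also labels the pre-hormone visits as baseline.

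**The plan's own sample size.** The target of 12 per phase is for a 25% fall in THC AUC (80% power, 5% alpha, paired). It cannot be reproduced because no SD or CV is given. Working back with a two-sided paired t-test, it implies an SD of log differences of |ln 0.75| / 0.889 = 0.2877 / 0.889 = 0.324. That is a within-subject SD of 0.324 / √2 = 0.229, or a CV of about 23%. No power is stated for heart rate or VAS.

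**What 12 completers give for a direct contrast.** For each woman, let D = (mean change from time 0 in the post-hormone session) − (the same in the control session). With SD denoting the SD of D:
- Normal approximation, two-sided 5%, 80% power: (1.960 + 0.842) / √12 = 2.802 / 3.464 = 0.81 SD.
- Exact paired t (noncentral t, 11 df): 0.89 SD. If all 16 enrolled women complete, 0.75 SD.
- Half-width of a 95% interval: 2.201 × SD / √12 = 0.64 SD.

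The documents give no SD for heart rate or VAS, so none of this can be put into beats per minute or VAS units.

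**Why within-session tests cannot stand in.** A simulation used 12 women, one post-dose time point, two-sided 5% tests and 40,000 runs. Effects are in SDs of the within-session change and are assumptions. With no hormone effect and the same true rise in both sessions:

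| True rise | Each session significant | One significant, the other not (between-session correlation 0.5 / 0) | Direct paired test significant |
|---|---|---|---|
| 0.4 SD | about 25% | 27% / 37% | 5% |
| 0.6 SD | about 47% | 35% / 50% | 5% |
| 0.85 SD | about 77% | 26% / 36% | 5% |
| 1.2 SD | about 97% | 6% / 7% | 5% |

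The zero-correlation column can be checked by hand as 2p(1 − p). For p = 0.475 this is 2 × 0.475 × 0.525 = 0.50.

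The error also runs the other way. With a real hormone effect (rise of 2.0 SD in one session and 1.2 SD in the other, correlation 0.5), both sessions are significant in 97% of trials and look alike. The direct paired test detects the difference in 72%.

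**The case against.** The strongest reply is that these outcomes are descriptive. The heart-rate text says so, the VAS title begins with the word *Description*, and comparing time points with baseline is a reasonable way to see whether the doses are active. Unlike the AUC outcomes, neither states a hypothesis about the hormone. Mean VAS will be shown for both sessions, so a side-by-side view exists for that measure. All of this stands. It does not remove the gap: the titles still name the with-and-without comparison, the heart-rate title promises to determine a magnitude, and the one formal test answers another question.

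Stronger readings that the documents do not support:
- *That the plan fails to run a promised test.* No hypothesis test of the hormone effect is promised for these two outcomes.
- *That the plan yields only lists of significant time points.* It also reports changes, their time course and, for VAS, means by session.
- *That the plan intends to compare significance between sessions.* Nothing says so; this is a risk in interpretation.
- *That counting post-dose time points gives a false-positive rate.* Such a calculation would treat serial readings that share one baseline as independent, and follow-up comparisons as unadjusted, which the plan does not say. It would not measure the missing contrast in any case.
- *That the contrast would isolate THC's effect.* There is no dronabinol-free session. That is a separate design limit, which a change to the analysis plan does not cure.

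**Conclusion.** The point holds as a gap in the secondary analyses. For heart rate and VAS, in both hormone phases, no estimate with a confidence interval and no test of the post-hormone versus control difference is planned. The planned ANOVA is suitable for describing dose activity and should stay for that purpose.

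The gap matters most if the THC response is modest. Under the assumed effects, sessions with equal true responses would disagree on significance in 26% to 50% of trials for rises of 0.6 to 0.85 SD, but in only 6% to 7% at 1.2 SD. These figures rest on assumed standardised effects and correlations, and on reading baseline as same-session time 0. The absence of the contrast rests on the text alone. The primary AUC analysis is unaffected.

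**What to change.** In the Statistical analysis plan:

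1. Define baseline for heart rate and VAS as time 0 of the same session.
2. For each hormone and measure, pre-specify one paired contrast: change from time 0 in the post-hormone session minus that in the same phase's control session. One option is the mean over 0–12 h, from a within-subject model with session, time and session-by-time terms and random effects for subject and for subject within session. Each phase needs its own control, because the Table of Study Events puts the two pre-treatment visits at different cycle days. For VAS, name the item or items that carry the contrast.
3. Report the contrast as an estimate with a confidence interval and label it secondary. With 12 completers only differences of about 0.89 SD or more have 80% power, so a wide interval must not be read as no effect.
4. Keep the time-versus-baseline results as description of dose activity, show heart rate by session as for VAS, and state that no hormone effect will be inferred from comparing significance between sessions.
5. State whether clock times are matched between paired sessions. Time-of-day effects cancel only if they are.

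Using change from same-day time 0 also helps because section 7 lists heart-rate and mood changes among the possible effects of hydrocortisone itself. It removes a constant shift, though not a hormone effect that varies during the day.

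If the team does not want the contrast, the minimum is to declare both outcomes descriptive and state that no hormone effect will be inferred from them. The cost is wording in the plan; no new visits, samples or subjects are needed.

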We expect a 50% change in THC clearance to be clinically significant and, based on existing data on CYP2C9 induction by glucocorticoids and estrogens, we predict the clearance of THC to be induced by 50% in our study by one or both of the hormonal exposures. Hence, we have powered our study to detect a 25% decrease in the AUC of THC. Based on the published variability in THC and its metabolite disposition and the variability in the magnitude of drug interactions measured, a paired power calculation for 80% power with an α (Type I error rate) of 5% results a **target number of subjects of 12 for each DDI study phase**. We intend to consent and enroll 16 subjects to undergo both study phases to ensure 12 subjects who complete all study procedures and have a wild type genotype for UGT1A1 and CYP2C9.

As a secondary outcome, we will determine the effects of estradiol and hydrocortisone treatment on the AUCs of 11-OH-THC, 11-nor-COOH-THC and the 11-nor-COOH-THC-glucuronide. Of these, 11-OH-THC is an active metabolite, and it has also been shown to be much more greatly affected by rifampicin induction than THC. Based on the published variability in the exposures to the THC metabolites, 12 subjects will also provide us with adequate power to determine whether the exposures to these metabolites are altered by estradiol or hydrocortisone. The changes in AUC will be tested using analysis of variance on log-transformed data. Point estimates and 90% confidence intervals will be defined for treatment versus control in THC disposition in accordance to the guidance on statistical analysis of DDI studies. To establish the difference between treatment and control, % confidence interval of the geometric means must be outside of the range of 0.80 to 1.25. If any of our subjects have a CYP2C9*2,*3 and UGT1A1*28 genetic polymorphism, we will also analyze the data for subjects with the specific genotype separately to avoid variability introduced by genetic polymorphisms.

3. Trial Management

The procedures will be conducted within the UW Institute of Translational Health Sciences (ITHS) Adult Translational Research Unit (TRU) and the UW Center for Research in Reproduction and

Contraception (CRRC), both of which are housed within the University of Washington Medical Center (hospital). There will be no other clinics or data collection centers involved.

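### The heart-rate and VAS comparisons at each time point use classical repeated-measures ANOVA with no stated contrast rule, sphericity handling or missing-reading rule; a mixed model with adjusted or purely descriptive contrasts would serve better

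*Combined protocol and SAP*

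**What the plan says.** For heart rate, Section 4 (Statistical analysis plan) states that "the change in heart rate at each time point after baseline will be compared to baseline by repeated-measures ANOVA". For the VAS it states that "the change in each subjective measure at each time point after baseline will be compared to baseline by repeated-measures ANOVA".

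The times come from the procedures description in Section 2: samples "will be collected at 0.5, 1, 1.5, 2, 3, 4, 6, 8, 10, 12 and 24 hours after THC dosing", which is 11 post-dose times. The same text adds: "At each time point, pharmacological biomarker analysis will also be performed". For the VAS, Secondary Outcome 3 says: "Subjects will complete VAS ratings at each of the blood sampling timepoints during the pharmacokinetic study visits". The Table of Study Events, however, marks vital signs on day 1 of each PK study only. The 24-hour reading falls on day 2 at a different clinic, so heart rate may have 10 post-dose times rather than 11.

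The sample-size section gives a "target number of subjects of 12 for each DDI study phase", with 16 women enrolled. Each woman has four PK sessions.

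On purpose, Secondary Outcome 2 (both hormone phases) calls the heart-rate data a descriptive measure of the size and duration of THC effects. It adds that they are to be used "to explore whether the doses used are pharmacologically active". Secondary Outcome 3 is headed as a description of side effects and psychoactive effects.

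For these comparisons the documents give no significance level, contrast method, multiplicity rule, overall test first, covariance or sphericity handling, or rule for missed readings. The QA and QC plan bars subjective omission of data and covers outliers, but it does not cover missed readings. The number of VAS scales is not stated.

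**The concern.** Three features of the stated method deserve attention.

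- **Many comparisons.** Each session yields up to 11 comparisons with one shared baseline, for heart rate and again for every VAS measure. Without a rule, isolated nominally significant times are to be expected.
- **Unequal spacing.** Gaps between readings run from 0.5 h to 12 h. Classical repeated-measures ANOVA assumes that every pairwise difference between times has the same variance. That is unlikely if nearby readings are more alike than distant ones.
- **Complete profiles.** In its conventional form the method needs every reading from a woman, and the last reading requires a next-day visit.

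What is at stake is the secondary description of how long dronabinol acts and whether this dose has a detectable effect. The primary THC AUC comparison does not depend on it.

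**Working it through.** **Plan's own figure.** There is none to reproduce. The plan states no error rate for heart rate or VAS, and its 12 women come from a calculation for THC AUC.

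**Inputs.** From the documents: n = 12 women; baseline plus 11 times at 0, 0.5, 1, 1.5, 2, 3, 4, 6, 8, 10, 12 and 24 h. Assumed: 5% two-sided per time point, no true effect, normally distributed readings. The correlation between readings is either equal for all pairs or exp(-gap/range) with range 1, 3 or 6 h.

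**Step 1: any false time point, per measure and session.** Eleven independent tests would give 1 - 0.95^11 = 43.1%. The shared baseline makes the tests positively correlated, so the true figure is lower and was simulated:

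| Correlation | Any false time point, no gate | Overall F, uncorrected | Any false time point, only if F is significant |
|---|---|---|---|
| Equal | 30-32% | 5% | 4% |
| Exponential, 1 h | 29-32% | 7% | 6% |
| Exponential, 3 h | 29-31% | 10% | 9% |
| Exponential, 6 h | 30-32% | 12% | 11% |

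The ranges in the second column cover paired t tests and contrasts using the pooled ANOVA error. With 10 post-dose times the ungated figure is 25-30%, depending on the correlation.

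The gate protects only when nothing happens at any time. With an assumed real effect of 1.2 SD from 1 to 6 h, the overall F is almost always significant. The chance of a false signal among the five remaining times (0.5, 8, 10, 12 and 24 h) is then about 18%.

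**Step 2: where the pooled error goes wrong.** With unit variance, the variance of (reading at t minus baseline) is 2(1 - exp(-t/range)). Classical ANOVA uses 2(1 - r) for every time, where r is the average correlation over all pairs. The ratio of true to assumed variance is (1 - exp(-t/range))/(1 - r):

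| Range | r | Ratio at 0.5 h | Ratio at 24 h | Error at 0.5 h | Error at 24 h |
|---|---|---|---|---|---|
| 1 h | 0.096 | 0.44 | 1.11 | 0.4% | 6% |
| 3 h | 0.277 | 0.21 | 1.38 | 0.0% | 10% |
| 6 h | 0.442 | 0.14 | 1.76 | 0.0% | 14% |

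Example at 6 h: (1 - exp(-24/6))/(1 - 0.442) = 0.982/0.558 = 1.76. The error columns are simulated against a nominal 5%. Early changes are thus hard to detect and late ones too easy to declare. This bears directly on any statement about onset or duration. Correcting the overall F for non-sphericity does not by itself repair contrasts that use the pooled error.

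**Step 3: incomplete profiles.** If each of 12 readings is missed independently with probability m, the share of women without a full set is 1 - (1 - m)^12.

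- m = 1%: 1 - 0.99^12 = 11%, leaving on average 10.6 of 12 women.
- m = 3%: 1 - 0.97^12 = 31%, leaving on average 12 × 0.694 = 8.3 of 12 women.

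The documents give no missing rate; 1-3% is an assumed range.

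**The case against.** The strongest reply is that these are declared descriptive and exploratory outcomes, so a stray significant time harms nothing that the trial is built to conclude. That stands as regards the primary THC AUC result, and it limits the weight of this point. It does not remove it. The plan attaches a test to every time point and uses the heart-rate data for duration and dose activity. If the purpose is purely descriptive, p-values are not needed; if they stay, their error should be controlled.

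Second, silence is not a rule. A reader might infer that one session in three will show a spurious effect, or, from 1 - 0.70^4 = 76%, that a false signal over four sessions is likely. The documents do not support either as a consequence of the plan. Both figures need 5% contrasts, no adjustment, no gate and no drug effect at all; the second also treats four sessions in the same women as independent. Repeated-measures ANOVA is often read as an overall test followed by contrasts, which gives 4-11% when there is no effect.

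A reader might also infer that dose activity and duration could both be established by chance. That goes too far. In ungated null simulations a false rise in heart rate at any time occurred in 15-16% of sessions. Two adjacent false rises, the least that would suggest a duration, occurred in 2-6%. All four sessions use the same dronabinol dose, which offers some replication.

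Third, loss of women through missed readings is only a possibility. No complete-case rule is stated, and 16 women are enrolled so that 12 complete all procedures. The plan likewise does not exclude a standard sphericity correction. All of this stands; what remains is that the named method is weaker than an available alternative and its details are unspecified.

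**Conclusion.** The point holds as a modest improvement to the analysis of secondary outcomes. The stated method suits unevenly spaced readings in about 12 women poorly, and the plan leaves contrast, adjustment and missing-reading handling open.

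The size depends on how the gaps are filled: about 29-32% per measure and session for unadjusted, ungated 5% contrasts with no effect, or about 4-11% with an overall-F gate. Under the assumed exponential correlation (range 1-6 h), the uncorrected F errs at 7-12%, and single contrasts range from about 0% at 0.5 h to 6-14% at 24 h. The time-dependent distortion is the more telling result, because it affects the duration reading and arises within each contrast, whether or not multiplicity is a worry.

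The correlation pattern and missing rates are assumptions; the documents give no data on either.

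**What to change.** In Section 4, replace repeated-measures ANOVA for heart rate and each VAS measure with a linear mixed model. Use time as a categorical effect, woman as a random effect, serial correlation based on elapsed time, and small-sample degrees of freedom. State that all available readings are used.

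Report the change from baseline at each time with a 95% CI. Either apply a Dunnett-type adjustment within each measure and session, or present the estimates as descriptive without p-values; say which in advance. State whether heart rate is taken at 24 h, so that the number of times is fixed, and list the VAS scales.

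A time-weighted mean change over 0-12 h may be added beside the time course and peak change. It should not replace them, since it cannot show duration, dilutes a short peak and leaves out the 24 h reading.

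The cost is SAP wording and standard software, with no new data. The downside is slightly wider intervals and fewer nominally significant time points.
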